#### 12.2 Site investigator assessment

The Principal Investigator is responsible for the care of the participant, or in their absence an authorised medic within the research team is responsible for assessment of any event for:

• Seriousness

Assessing whether the event is serious according to the definitions given in section 0.

#### Causality

Assessing the causality of all serious adverse events/reactions in relation to the study treatment according to the definition given. If the SAE is assessed as having a reasonable causal relationship, then it is defined as a SAR.

• Expectedness

Assessing the expectedness of all SARs according to the definition given. If the SAR is unexpected (as per the RSI), then it is a SUSAR.

• Severity

Assessing the severity of the event according to the following terms and assessments. The intensity of an event should not be confused with the term "serious" which is a regulatory definition based on participant/event endpoint criteria.

- **Mild**: Some discomfort noted but without disruption of daily life
- Moderate: Discomfort enough to affect/reduce normal activity
- Severe: Complete inability to perform daily activities and lead a normal life

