#### 7.5.4 Follow-up (visits 4-7)

Patients will be monitored on a 4-weekly basis as shown in the study visit schedule (Table 1), Section 8.2). Patients will be followed up to 16 weeks. If the study is running at the particular site, there is a potential for patients to be recruited into a long term follow up study: CReMSIA (REC ref: 17/EE/0119). Data collection in the CReMSIA study will be recorded in an electronic CRF. Patients will be followed up as per best practice as currently done in the academic centre participating in the trial.

Safety blood tests will be undertaken every 4 weeks. Additional blood tests for monitoring of toxicity/safety of therapy may be undertaken at the physician's discretion. The ACR 50, a validated composite end point, will be used to assess response to therapy as the primary outcome measure. The Health Assessment Questionnaire, EQ-5D-5L and SF-36 will be used to gauge functional ability and improvement in other aspects of the patients' life. The ESS will be used to measure a patient's sleepiness.

Visits 4 - 7 will be carried out every 4 weeks (±7 days) from the baseline visit. The Principal Investigator will need to review any non-compliance with a view to withdrawing patients at their discretion if drug schedule is adversely affected. Patients who consent to the biopsy procedure at Visit 7 (Week 16) will be asked to complete the Pre Biopsy Assessment Form at Visit 7 (week 16) and the Post Biopsy Assessment Form at the safety follow up visit. If the safety

follow-up visit is completed over the phone, this questionnaire will be completed over the phone.

As per normal clinical practice, the GPs of participants with active RA and a cardiovascular risk profile will be informed and asked to review treatment.

All joint assessments from baseline will be performed by a member of the local trial team who will be blinded to treatment allocation. The joint assessor should also complete the VAS physician assessment component of the VAS Pain Score questionnaire. Data will be entered in the electronic CRF by the Investigator or designee who will also coordinate data validation checks and query resolution.

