#### Laboratory Evaluations and Study Sample Collection

#### 7.6.13 Local Blood Sampling

Bloods will be taken for local laboratory investigations at each clinic visit as per the study visit schedule. These include ESR, CRP, Haematology (Hb, Haematocrit, WBC, platelet count, neutrophils, lymphocytes, Red blood cell count, Mean cell haemoglobin, Mean cell volume), and Biochemistry (Urea, sodium, Creatinine, potassium, ALT, AST).

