## 12.0 Pharmacovigilance

#### **12.1 General definitions**

Term	Definition
Adverse Event (AE)	Any untoward medical occurrence in a participant to whom a medicinal product has been administered, including occurrences which are not necessarily caused by or related to that product.
Adverse Reaction (AR)	An untoward and unintended response in a participant to an investigational medicinal product which is related to any dose administered to that participant. The phrase " response to an investigational medicinal product " means that a causal relationship between a study medication and an AE is at least a reasonable possibility, i.e. the relationship cannot be ruled out. All cases judged by either the reporting medically qualified professional or the sponsor as having a reasonable suspected causal relationship to the study medication qualify as adverse reactions.
Serious Adverse Event (SAE)	
 
A serious adverse event is any untoward medical occurrence that:
 
Results in death.
 
Is life-threatening.
 
Requires inpatient hospitalisation or prolongation of existing hospitalisation (excludes day cases)
 
Results in persistent or significant disability/incapacity.
 
Consists of a congenital anomaly or birth defect.
 
Other 'important medical events' may also be considered serious if they jeopardise the participant or require an intervention to prevent one of the above consequences.
 
NOTE: The term "life-threatening" in the definition of "serious" refers to an event in which the participant was at risk of death at the time of the event; it does not refer to an event which hypothetically might have caused death if it were more severe.
 

Serious Adverse Reaction (SAR)	An adverse event that is both serious and, in the opinion of the reporting Investigator or medical assessor, believed with reasonable probability to be due to one of the study treatments, based on the information provided.

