#### 14.9 Safety analysis

The safety analysis set consists of patients who received at least one dose of the trial medication. Safety analysis will be based on the safety analysis set. All AEs will be recorded, notified, assessed for seriousness, and severity, reported, analysed and managed in accordance with the Medicines for Human Use (Clinical Trials) Regulations 2004. The reporting and notification of serious adverse events (SAEs) and suspected unexpected serious adverse reactions (SUSARs) is specified in the protocol and these events will be summarised by treatment and pathotype.

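### The only AE severity scale has no criterion for laboratory abnormalities: a symptom-free ALT rise or cytopenia fits no grade, or defaults to mild, whatever its size

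*Protocol*

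**What the plan says.** Section 12.2 makes the site investigator responsible for assessing any event for seriousness, causality, expectedness and severity. The severity instruction, printed under the Causality sub-heading, reads "Assessing the severity of the event according to the following terms and assessments". Three grades follow. The lowest, mild, is given as "Some discomfort noted but without disruption of daily life". The middle grade is reached when the discomfort limits what the patient would usually do. The top grade is worded as "Complete inability to perform daily activities and lead a normal life".

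The same section warns that intensity and seriousness are different things. On seriousness, section 12.1 adds a category that does not depend on symptoms: "Other 'important medical events' may also be considered serious if they jeopardise the participant or require an intervention".

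On monitoring, section 7.5.4 says "Safety blood tests will be undertaken every 4 weeks". Section 7.6.13 lists the local tests as ESR, CRP, full haematology including neutrophils, lymphocytes and platelets, and "Biochemistry (Urea, sodium, Creatinine, potassium, ALT, AST". Section 14.9 closes the chain: "All AEs will be recorded, notified, assessed for seriousness, and severity, reported, analysed".

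**The concern.** The trial's laboratory monitoring looks for harms that often cause no symptoms when detected, whereas the severity scale recognises only symptoms and their effect on activity. All patients are DMARD-naive and start methotrexate with escalation over the first 4 to 6 weeks (7.5.6), and half also receive abatacept. Transaminase rises and falls in blood counts are therefore among the AEs that investigators may have to grade.

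If the grade cannot respond to the size of the abnormality, it carries no information about intensity for these events. Section 14.2 plans at least 10 centres in an international trial. Some investigators may enter mild, some may apply a scale of their own, and some may leave the field blank. Severity would then vary with local habit as well as with the event.

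**Working it through.** No arithmetic underlies the point. It is a reading of the scale against the tests that it must serve.

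1. **Scope.** Section 12.2 applies to any event and gives one scale, with no exception for laboratory findings.

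2. **Apply the scale to an AE that is an ALT rise or a low cell count without symptoms.**
   - Severe requires complete loss of daily function: not met.
   - Moderate requires discomfort that limits activity: not met.
   - Mild has two parts. Daily life is undisturbed: met. Some discomfort is noted: not met.
   - Result: no grade fits. Mild is nearest because one of its two parts is met.

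3. **Vary the size of the abnormality.** No condition in step 2 contains the laboratory value, a reference limit or a need for intervention. A small rise and a very large one, both without symptoms, give the same result.

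4. **Vary the symptoms.** A cytopenia with a disabling infection can meet moderate or severe. The gap is therefore confined to abnormalities without symptoms or functional loss.

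5. **Look for another criterion.** The protocol contains no toxicity grading system, no multiple of a reference limit and no cell-count threshold for AE grading. Sections 11.12 and 11.13 refer to the SmPC for dose adjustment and for management of abatacept-specific events, and 12.3 uses it for expectedness. None of these concerns severity grading.

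6. **Opportunities for such an AE.** The schedule in 7.2 places haematology and biochemistry at weeks 4, 8, 12 and 16 after baseline. With the planned 200 randomised patients, 200 × 4 = 800 scheduled post-baseline panels at most. This counts measurements, not AEs. The protocol gives no rate of abnormal values and none for how many would be recorded as AEs, so the number affected cannot be derived.

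7. **Where the grade is used.** Section 14.9 has every AE assessed for severity and analysed. The SUSAR definition in 12.1 compares the nature and severity of a serious reaction with the reference safety information, so the scale matters there only if the laboratory event is serious. The only safety endpoint, in 2.4, is exploratory and counts SAEs, which depends on seriousness.

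**The case against.** The strongest reply is that little is lost. An important symptom-free event can be reported as serious through the important-medical-event category in 12.1. Section 7.5.4 allows extra toxicity bloods at the physician's discretion. The eCRF is to record all required assessments at each visit (15.2), so laboratory values can be compared between arms whatever severity is entered. No endpoint uses the severity grade, and this is a Phase IV, Type A trial written on a sponsor template. All of this stands, and it sets the limits of the point. It does not repair the severity variable: the serious-event route is a matter of judgement, and 12.2 itself keeps seriousness apart from intensity.

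Three stronger readings are tempting, and the document supports none of them:

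- A reader might infer that laboratory harms can only ever be graded mild. The text does not say so. Mild also requires discomfort, and events with symptoms can be graded higher.
- A reader might infer that section 14.9 will tabulate severity by arm and so make one arm look safer. It states no such table. The strata it names are treatment and pathotype, in the sentence on SAEs and SUSARs.
- A reader might take the lack of a laboratory analysis in 14.9 as a gap. Section 14.4 leaves analysis detail to the SAP, so its absence here is no fault.

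**Conclusion.** The point holds within narrow limits. The protocol fixes a severity scale that cannot grade a symptom-free laboratory abnormality in any informative way. This is a stated rule for sites to follow during the trial, not a detail left to the SAP. The damage is to the severity data for non-serious, symptom-free laboratory AEs: uninformative at best, inconsistent between sites at worst. The primary analysis, the exploratory SAE endpoint and the laboratory values are unaffected.

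The conclusion rests on the wording of 12.2 and on the absence of any other grading criterion in the protocol. It needs no assumed event rate, and a patient count would be guesswork. Default grading as mild and differences between sites are expected behaviour where no category applies; the protocol does not state them.

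**What to change.** In section 12.2, keep the functional scale for symptomatic events. Add that an AE consisting of an abnormal laboratory value is graded from the recorded value, relative to the local reference limit, on a recognised numeric toxicity scale chosen by the sponsor and named in the protocol. State that this grade is used wherever AE severity is reported. It can be derived centrally from values already collected, which would also remove variation between sites.

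The cost is protocol wording and one derived variable, with no new sample or visit. The downside is small: tests are run in local laboratories, so the reference limits must be stored with each value.

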#### **12.3 Reference Safety Information (RSI)**

Reference Safety Information (RSI) section 4.8 is the information used for assessing whether an adverse reaction is expected. For this trial, the RSI for abatacept will be the current and most updated version of the Orencia 125 mg solution for injection in pre-filled pen – SmPC.

# 12.4 Notification and recording of Adverse Events (AEs) or Reactions (ARs)

All AE and AR's are to be documented in the participants' medical notes or other source data documents and the CRF. Once assessed, if the AE is not defined as SERIOUS, the AE is recorded in the eCRF and the participant is followed up by the research team until the AE is considered resolved.

AEs and Serious Adverse Events (SAEs) should be recorded from the time that the first trial specific assessment/procedure is undertaken (screening visit), and then subsequently at follow-up visits throughout duration of trial treatment. Participants should be advised to notify the trial site of any untoward medical events as soon as possible, even if this is outside of their normal visit schedule.

AEs and SAEs should continue to be reported, following the same reporting procedures, throughout the patient's time on the trial and for a further 30+ days after the week 16 visit (or their last dose of IMP, if earlier).

An AE would usually be considered resolved once the main symptoms are no longer present or once the patient is receiving treatment and the event is considered stabilised. If a patient has a new long-term diagnosis made during the trial, this should be documented as recovered with sequalae once the patient is considered stable and the condition is being adequately treated (if applicable), even if the diagnosis is ongoing (for example, if a patient has a new diagnosis such as diabetes during the trial). SAE's resulting in hospitalisation will be considered resolved once the patient is sufficiently recovered enough to be discharged from hospital.

#### 12.4.1 Adverse Events notification to BMS

Non-serious Adverse Events (AE) are to be provided to BMS in aggregate via interim or final study reports as specified in the agreement or, if a regulatory requirement as part of an annual reporting requirement.

#### 12.5 Adverse events that do not require reporting

The following events are not considered as SAEs for the trial:

- Pregnancy (however it is an event that requires monitoring and follow up- pregnancy CRF must be completed)

- Procedures that were planned prior to the screening visit (although this does not exclude any complications post-procedure)

- Pre-existing conditions prior to the screening visit, unless the condition has worsened

Note: The following definition **is** considered a SAE for this trial:

- Elective surgery at any time, which is related to, or has resulted from, any new or worsening condition.

# 12.6 Notification and Reporting of Serious Adverse Events (SAEs) and Suspected Unexpected Serious Adverse Reactions (SUSARs)

All Serious Adverse Event (SAEs) and Suspected Unexpected Serious Adverse Reactions (SUSARs) will be recorded in the participants' notes, the eCRF, the sponsor SAE form and reported to the sponsor (administered by the Joint Research Management Office or agreed representative) within 24 hours of the site becoming aware of the event.

Nominated co-investigators (as listed in the delegation log for each site) will be authorised to sign the SAE forms in the absence of the PI at the participating sites.

#### 12.6.1 SAEs and SUSARs notification to BMS

All Serious Adverse Events (SAEs) that occur following the subject's written consent to participate in the study through *30* days of discontinuation of dosing must be reported to BMS Worldwide Safety, whether related or not related to study drug. **If applicable**, SAEs must be collected that relate to any follow-up protocol-specified procedure.

SAEs, whether related or not related to study drug, and pregnancies must be reported to BMS within 24 hours \ 1 Business Day of becoming aware of the event. SAEs must be recorded on either CIOMS, MedWatch, or approved study specifi/institutional SAE form.

If only limited information is initially available, follow-up reports are required.

If an ongoing SAE changes in its intensity or relationship to study drug or if new information becomes available, a follow-up SAE report should be sent within 24 hours \ 1 Business Day to BMS using the same procedure used for transmitting the initial SAE report.

All SAEs should be followed to resolution or stabilization.

#### 12.6.2 Procedures for reporting blinded SUSARs

The CI, as sponsor medical assessor, will assess the event blinded for all possible IMPs, placebos, and combinations.

The Joint Research Management Officer (JRMO) at Queen Mary University of London will be unblinded to facilitate unblind SUSAR reporting to the MHRA. A delegated and trained JRMO will have access by an account with limited access to the Early RA 3TR Database to unblind the participants independently. The IT Systems and Project Manager will report the IMP to Joint Research Management Officer to enable them to report to MHRA in case of issues in accessing the Database from the delegated JRMO.

A delegated member from the clinical team will be responsible for maintaining unblinded records for the trial. This will be recorded in the delegation log for the study.

#### **12.7 Sponsor medical assessment**

Sponsor has delegated the responsibility for oversight of IMP safety profile and medical assessment of AEs, ARs, SAEs and SUSARs to the CI as medical assessor The CI must review all SAEs within 72 hours of receipt. This review should encompass seriousness, relatedness, and expectedness. Day 0 for all SUSARs is when the SAE / SUSAR is received by the CI and / or coordinating team and / or sponsor (whichever is first).

It is noted that the CI cannot downgrade the PI assessment of an event's causality. If there is disagreement between CI and PI assessment, no pressure should be placed on the PI to alter their assessment, but the CI can liaise with the site PI before the CI's final decision. The CI and PI assessment can differ.

The CI's assessment will be documented directly on the eCRF.

#### 12.8 Urgent safety measures

The CI may take urgent safety measures to ensure the safety and protection of the clinical study participants from any immediate hazard to their health and safety, in accordance with Regulation 30 of the Medicines for Human Use (Clinical Trials) regulations. The measures should be taken immediately. In this instance, the approval of the Competent Authority prior to implementing these safety measures is not required.

The CI has an obligation to inform both the MHRA and Research Ethics Committee in writing **within 3 days** of implementing the Urgent Safety Measure. They must also submit a substantial amendment documenting the changes with 14 days of implementing the urgent safety measure. The JRMO must be sent a copy of the correspondence with regards to this matter as soon as it is sent.

#### 12.9 Pregnancy

If a participant becomes pregnant whilst involved in a CTIMP, it is not considered to be an SAE or an AE.

However, it is an event that requires reporting, monitoring and follow up. If a participant or participant's partner becomes pregnant whilst or after taking an IMP, the sponsor should be notified immediately (within 24 hours of site becoming aware of the pregnancy) using the

sponsor pregnancy form. The pregnancy reporting procedure will be the same as the SAE reporting route. Pregnancy should be reported via a paper form and should be sent to [contact]

The CI (in conjunction with the site PI) should determine if the foetus has been exposed to an IMP. The PI has the responsibility to ensure that the pregnancy form is completed and sent to the sponsor within the agreed timelines. The initial report should be sent within 24 hours of the PI or co-investigator becoming aware of the event and follow up information submitted as and when it becomes available up to agreed follow up time after birth. For patients receiving abatacept pregnancies will also be reported to the IMP provider (BMS).

The sponsor will arrange for a review of the pregnancy report by an appropriate expert medic (usually a consultant obstetrician). The study team must follow all instructions provided by the sponsor's expert.

In the event of pregnancy, the patient must be withdrawn from the trial interventions and may attend follow ups as per scenario for patients ceasing treatment prior to 16 weeks subject to continued consent.

The PI/CI also must follow up the pregnancy until delivery as well as monitoring the development of the new-born for one month after birth. Any events that occur during this time that could be considered to be a SAE must be reported to the sponsor in line with section 12.7, utilising the SAE CRF reporting form.

#### 12.9.1 Pregnancy notification to BMS

The Sponsor-Investigator must immediately notify BMS of this event and complete one of the following forms **within 24 hours of awareness** of the event via either the CIOMS, MedWatch or appropriate Pregnancy Surveillance Form in accordance with **SAE reporting procedures**.

Follow-up information regarding the course of the pregnancy, including perinatal and neonatal outcome and, where applicable, offspring information must be reported on the **approved site SAE form**.

Any pregnancy that occurs in a female partner of a male study participant should be reported to BMS. Information on this pregnancy will be collected on the Pregnancy Surveillance Form. In order for Sponsor-Investigator or designee to collect any pregnancy surveillance information from the female partner, the female partner must sign an informed consent form for disclosure of this information.

## 13.0 Annual reporting

### 13.1 Development Safety Update Report (DSUR)

The DSUR will be written by the CI (following Sponsor procedures) and submitted to the sponsor for review prior to submission to the MHRA. The DSUR is due for submission within 60 days of the end of the reporting period. The reporting period is annually from the date on the "*Notice of acceptance letter*" from the MHRA. The sponsor's delegated Medical Assessor, usually the CI, will carry out a risk benefit analysis of the IMPs encompassing all events having arisen on the study. REC will be sent a copy of the DSUR.

The DSUR will be submitted through the CTIS system by the Coordinating Trials office to non-UK Competent Authorities or will be sent to the competent authority by the Lead research team in that country. The lead research team in each country will be responsible for reporting to their ethics committees.

